7.7.3.2 Urine Drug Screen

A urine sample for the following assessments will be collected at the Screening visit: amphetamines, barbiturates, benzodiazepines, cocaine, opiates, phencyclidine and tetrahydrocannabinol.

Results from the urine drug screen will be listed for the Safety population.

7.7.3.3 Urine Pregnancy Test

A urine dipstick pregnancy test will be performed on all female patients at the Screening visit.

Pregnancy screen results will be listed for the Safety population

7.7.4 Vital Signs

The following vital signs will be listed and summarized by treatment group and visit.

- systolic blood pressure (mmHg);
- diastolic blood pressure (mmHg);
- pulse rate (bpm);
- respiratory rate (breaths/min);
- body temperature (°C);
- weight (kg)
- height (m)
- BMI (kg/m²).

Vital signs data and changes from baseline in vital signs will be summarized by visit using standard descriptive statistics for the Safety population.

All vital sign data collected for the Safety population will be listed.

7.7.5 Electrocardiograms

The following quantitative ECG measurements will be taken during the study:

- heart rate (bpm);
- PR interval (msec);
- QRS interval (msec);

Statistical Analysis Plan

Sponsor Name: Insys Development Company, Inc.
Sponsor Protocol ID: INS011-16-085

Covance Study ID: 000000163564

- QT interval (msec);
- QTcF interval (msec)
- RR interval (msec).

An overall Investigator assessment of ECG will be provided (categories "normal", "abnormal, not clinically significant" and "abnormal, clinically significant").

The ECG measurements and changes from baseline in ECG will be listed and summarized by treatment group and visit using standard descriptive statistics for the Safety population.

The Investigator assessment will be listed and the number and percentage of patients within each assessment category will be tabulated by treatment group and visit for the Safety population. Shifts from baseline at each post-baseline visit will be presented.

A listing of ECG measurements and findings will be produced for the Safety population.

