3.2. Patient Selection

3.2.1. Inclusion Criteria

All patients must satisfy the following criteria to be considered for study participation:

1. Patient and/or parent(s)/caregiver(s) fully comprehend the informed consent form (ICF) and assent form, understand all study procedures, and can communicate satisfactorily with the investigator and study coordinator, in accordance with applicable laws, regulations, and local requirements.
2. Males and females from 8-17 years of age, inclusive.
3. Genetically confirmed diagnosis of Prader-Willi Syndrome using standard DNA methylation test or fluorescent *in situ* hybridization. Documentation of genetically confirmed diagnosis of Prader-Willi Syndrome is acceptable.
4. A score of ≥ 10 on the HQ-CT.
5. A caregiver is available to complete the HQ-CT.
6. If female, is either not of childbearing potential (defined as premenarchal or surgically sterile [bilateral tubal ligation, bilateral oophorectomy, or hysterectomy]) or practicing one of the following medically acceptable methods of birth control:
 - a. Hormonal methods such as oral, implantable, injectable, vaginal ring, or transdermal contraceptives for a minimum of 1 full cycle (based on the patient's usual menstrual cycle period) before study drug administration.
 - b. Total abstinence from sexual intercourse since the last menses before study drug administration.
 - c. Intrauterine device.
 - d. Double-barrier method (condoms, sponge, or diaphragm with spermicidal jellies or cream).
7. Adequate renal function, defined as serum creatinine $\leq 1.5 \times$ upper limit of normal (ULN) and urine protein/creatinine ratio < 0.2 .
8. Adequate hepatic function, defined as total bilirubin $\leq 1.5 \times$ ULN and aspartate aminotransferase (AST) and Alanine aminotransferase (ALT) levels $\leq 3 \times$ ULN.
9. Growth hormone treatment will be permitted if doses have been stable for at least 1 month prior to screening.
10. Psychotropic treatment will be permitted and should be stable at least 6 weeks prior to screening.
11. Any other treatment including thyroid hormones should be stable for at least 6 weeks prior to screening.

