6.2.6.9. Special Considerations

Cannabidiol inhibits drug metabolism mediated by a subset of CYP proteins (see [Section 1.1.2](#)). Thus, the Investigator and study center staff should monitor patients who are taking concomitant medications that are metabolized by CYP2C19, CYP2C9, CYP2D6, CYP3A4, CYP1A2 or by P-glycoprotein with special care.

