8.6.4.4. Electrocardiograms

For the continuous ECG parameters, descriptive statistics will be presented for values collected during Screening, and Treatment Period Visits, and for the changes from Screening to Study Completion/Early Withdrawal.

The following ECG parameters will be reported for this study: HR (Ventricular rate) (bpm), PR Interval (msec), QRS Interval (msec), QT Interval (msec), QTcF Interval (msec) (QT interval corrected by Fridericia), RR Interval (msec), Rhythm (Sinus rhythm, Atrial fibrillation, Other), Overall assessment of ECG (Normal, Abnormal, Not Clinically Significant [ANCS], Abnormal, Clinically Significant [ACS]).

Additionally, the number and percentage of patients will be presented as shift tables for the overall interpretation from Screening (normal or abnormal, not clinically significant [NCS]) to Study Completion/Early Withdrawal (normal; abnormal, NCS; or abnormal, clinically significant [CS]).

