7.1 General Principles

All data processing, summarization and analyses will be performed using Covance's SAS Environment / Version 9.4 (or later) of the SAS® statistical software package.

The analysis treatment group will be defined by the modal dose of study drug (dose of the study drug that the patient took for the longest period).

Statistical Analysis Plan

Sponsor Name: Insys Development Company, Inc.
Sponsor Protocol ID: INS011-16-085

Covance Study ID: 000000163564

The following principles will be applied to all TFLs unless otherwise stated:

Principle	Value
Significant tests	Two-sided and use a 5% significance level for main effects and 10% significance level for interaction terms
Treatment group labels and order presented	Listings: Placebo Cannabidiol Oral Solution (30 mg/kg/day) Cannabidiol Oral Solution (40 mg/kg/day) Tables: Placebo CBD (30 mg/kg/day) CBD (40 mg/kg/day) All CBD Total
Tables	Data in summary tables presented by treatment group and visit (where applicable)
Listings	All data collected presented by Treatment group Patient Visit (where applicable) Date; unless otherwise specified
Descriptive summary statistics for continuous variables	Number of patients/observations (n) Mean Standard deviation (SD) Median Minimum Maximum

COVANCE INC. CONFIDENTIAL

Document Date: 9 July 2018

Page 17 of 39
ST-AD-008 version 04

Downloaded by PPD on 10/12/2022

Statistical Analysis Plan

Sponsor Name: Insys Development Company, Inc.

Sponsor Protocol ID: INS011-16-085

Covance Study ID: 000000163564

Principle	Value
Descriptive summary statistics for categorical variables	Frequency counts and percentages [n (%)]
Denominator for percentages	Number of patients in the analysis population, unless stated otherwise in table shell(s)
Include "Missing" as category	Yes, when the number missing is greater than zero for at least one treatment group
Display for 0 percentages	Leave blank
Display to one more decimal place than collected value	Mean Mean Difference Median Percentages
Display to two more decimal places than collected value	Standard Deviation Confidence Interval
Limit of precision for displays	3 decimal places
Date Format	DDMMYYYY

Baseline is defined as the last scheduled or unscheduled measurement collected prior to first dose of double-blind investigational medicinal product (IMP) treatment.

Only data from scheduled post-baseline visits will be included in analyses and summary tables, all visit data will be listed.

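### No planned ECG table counts, by arm, how many patients had a large QTcF value or increase, and unscheduled post-baseline ECGs enter no summary at all

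*SAP*

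**What the plan says.** Both documents treat the 12-lead ECG as a safety endpoint and list QTcF among the parameters. ECGs are scheduled at Screening, Week 5, Week 9 and Week 13/Early Withdrawal (Protocol 6.2.4).

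- **Continuous summary.** SAP 7.7.5: "The ECG measurements and changes from baseline in ECG will be listed and summarized by treatment group and visit using standard descriptive statistics". SAP 7.1 gives the content of those statistics: "Number of patients/observations (n) Mean Standard deviation (SD) Median Minimum Maximum". Protocol 8.6.4.4 agrees: "For the continuous ECG parameters, descriptive statistics will be presented for values collected during Screening, and Treatment Period Visits", together with changes from Screening to the end of the study.
- **Categorical summary.** SAP 7.7.5: "The Investigator assessment will be listed and the number and percentage of patients within each assessment category will be tabulated by treatment group and visit", with shifts from baseline. Its three categories are normal, abnormal not clinically significant, and abnormal clinically significant. Protocol 8.6.4.4 likewise: "the number and percentage of patients will be presented as shift tables for the overall interpretation from Screening". Neither document attaches a number to a category.
- **Listings.** SAP 7.7.5 lists ECG measurements and findings for the Safety population.
- **Unscheduled ECGs.** SAP 7.1 lets an unscheduled pre-dose measurement serve as baseline. After baseline, it restricts analyses and summary tables to scheduled visits and leaves the rest to listings.

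On co-medication, Protocol 3.2.1 states: "Psychotropic treatment will be permitted and should be stable at least 6 weeks prior to screening". Protocol 6.2.6.9 states: "Cannabidiol inhibits drug metabolism mediated by a subset of CYP proteins", and asks for special care with drugs cleared by those enzymes.

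**The concern.** Means by visit describe a shift of the whole arm well. They describe a large change in a few patients poorly, because the rest of the arm dilutes it. This trial allows stable psychotropic treatment alongside a drug that inhibits several CYP enzymes, so an effect limited to some co-medicated children is conceivable. The natural summary for that pattern is a count of patients by arm, and none is planned for any ECG interval. The laboratory data do get one: SAP 7.7.3.1 plans reference-range shift tables for hematology and chemistry.

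At stake is how well the report can answer a simple safety question: how many patients in each arm had a large QTcF value or increase at any time on treatment? Without pre-specified categories, the count would have to be built from listings after unblinding, with cut-offs chosen once the data are known. The rule on unscheduled visits adds to this. A repeat ECG prompted by a doubtful reading would be listed but would not reach any table, including the maximum.

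**Working it through.** **Step 1: which planned output could give the count?** The documents contain no QTcF figure to reproduce, so the first check is a reading of each output.

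- *Mean, SD, median by visit:* no count.
- *Minimum and maximum by visit:* show the most extreme value and change at that visit, but not how many patients were affected. Nor can visits be combined: a maximum change of 60 ms at each of Weeks 5, 9 and 13 could be one child three times or three children once each.
- *Investigator's overall reading:* counted by arm, but it covers the whole ECG and has no numeric rule.
- *TEAE tables (SAP 7.7.2):* count a prolonged QT by arm only if the investigator reports it as an adverse event.
- *Listings:* contain every value, but no tabulation.

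None gives the number of patients by arm above a QTcF value or an increase.

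**Step 2: how far would a few patients move the mean?** The arm size of 33 is from SAP 2.3. The 60 ms rise and the SD of QTcF change (12, 15, 20 ms) are assumptions.

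Mean shift = k × 60/33:
- k = 1: 60/33 = 1.8 ms
- k = 2: 120/33 = 3.6 ms

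Standard error of the between-arm difference = SD × √(2/33) = SD × 0.246:
- SD 12: 3.0 ms
- SD 15: 3.7 ms
- SD 20: 4.9 ms

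For k = 2 the shift is 3.64/2.95 = 1.2 standard errors at SD 12 and 3.64/4.92 = 0.7 at SD 20. For k = 1 it is 0.6 and 0.4.

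**Step 3: let the affected patients also widen the CBD SD.** SD of the CBD arm = √(s² + 60² × p(1 − p)), with p = k/33 and s the SD in the other patients.

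| s (ms) | k | CBD SD (ms) | SE of difference (ms) | Shift/SE |
|---|---|---|---|---|
| 15 | 1 | 18.2 | 4.1 | 0.44 |
| 15 | 2 | 20.7 | 4.5 | 0.82 |
| 20 | 1 | 22.5 | 5.2 | 0.35 |
| 20 | 2 | 24.6 | 5.5 | 0.66 |

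The means still do not show it. The SD does move (15 to 20.7 ms in the second row), and the maximum would be large. A count table would read 1/33 (3.0%) or 2/33 (6.1%).

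**Step 4: fewer ECGs at later visits.** With the planned 20% dropout, 33 × 0.8 = 26.4 per arm remain. At 26 per arm, two such patients move the mean by 120/26 = 4.6 ms, against a standard error of 3.3 ms (SD 12) to 5.5 ms (SD 20). That is 1.4 to 0.8 standard errors, so the conclusion is unchanged.

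**Step 5: how noisy would a count table be?** Assume normal changes with mean zero. The chance of exceeding +30 ms at one visit is 0.6%, 2.3% or 6.7% for SD 12, 15 or 20. For the worst of three visits, 1 − (1 − p)³ gives 1.9%, 6.7% or 18.7%, or about 0.6, 2.2 or 6.2 of 33 per arm. Independence between visits makes these upper bounds. For +60 ms at SD 20 the chance is 0.13% per visit and 0.4% over three, about 0.1 patient per arm. The lower category is noisy; the higher one is nearly clean.

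**The case against.** Much of the case on the other side stands.

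- **The data are not lost.** About 66 patients with four scheduled ECGs give at most 264 listed records, showing treatment group, QTcF and change from baseline. Anyone can count from them. That is correct; what is missing is a count with categories fixed in advance.
- **The planned cells would react.** A reader might infer that the trial could report no QTcF difference while several CBD patients had large increases. The documents do not support that. The SD and maximum are planned for changes as well as values, and step 3 shows the SD rising visibly. They would signal that something happened at a visit, though not in how many patients overall.
- **No test is planned.** Safety is descriptive (Protocol 8.6.4), so the standard error is only a yardstick for reading the means.
- **The mechanism is not in the documents.** A reader might infer that CBD, through interactions, is expected to prolong QT. Neither document says so, and no QT-prolonging psychotropic is named. Protocol 1.3.3 cites studies with no ECG changes, though at doses well below 40 mg/kg/day. Protocol 3.2.2 excludes clinically significant ECG abnormalities. Protocol 4.7.2 restricts strong inhibitors and certain other interacting drugs, but only for CYP3A4 and CYP2D6. Protocol 6.2.6.9 names further enzymes, so interacting co-medication remains possible.
- **Counts would not settle it either.** Two of 33 against none gives a two-sided Fisher p of 2 × (33 × 32)/(66 × 65) = 0.49. True, but the table is meant to describe, not to test.

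**Conclusion.** The gap is real and modest. Listings, descriptive statistics of values and changes, and counts of an overall reading are all planned. A count by arm of patients with a large QTcF value or increase at any post-baseline visit is not, and unscheduled post-baseline ECGs enter no summary table.

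If 1 or 2 of 33 CBD patients rose by 60 ms, the mean would move by 1.8 or 3.6 ms against a standard error of about 3 to 5 ms, and so would not reveal it. This rests on the assumed rise and SDs; neither is in the documents. The maximum and SD could raise the question but could not answer how many.

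It would go too far to say that such patients would be invisible or that an interaction effect on QT is expected. The documents support only that an effect confined to a few patients is possible. Nothing here touches the primary analysis, sample size or alpha. I grade it a cheap improvement, optional rather than critical.

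**What to change.** Before unblinding, add one descriptive table to SAP 7.7.5 for the Safety population, with columns for placebo and all CBD:

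- n (%) of patients by worst post-baseline QTcF, for example >450, >480 and >500 ms;
- n (%) of patients by largest increase from baseline, for example >30 and >60 ms.

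These cut-offs are suggestions for analysis only. They come from neither document and are not management rules; the sponsor should fix its own before unblinding. Use as denominator the patients with at least one post-baseline ECG (and a baseline ECG for the increases), and show it. State that unscheduled post-baseline ECGs count in this table, as an explicit exception to the scheduled-visits rule in SAP 7.1. I would not split the table by psychotropic use: with 33 per arm the cells would be too sparse to help, and the listings allow a look at individual patients.

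The cost is one table from data already collected, with no new visits, testing or change in sample size. The downside is a few more untested counts. The lowest increase category will contain chance exceedances in both arms (step 5), so it should be read against placebo and not on its own.

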7.7.6 Physical Examination

Physical examination results (normal/abnormal) and details of abnormalities will be listed for the Safety population.

For each physical examination body system, the number and percentage of patients with abnormalities at baseline and post-baseline will be summarized by treatment group for the Safety Population.

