1.4. Prader-Willi Syndrome

Prader-Willi Syndrome (PWS), first described in 1956, is a multifaceted developmental disorder and the most common genetic syndrome associated with obesity (Gunay-Aygun et al., 1997; McAllister and Whittington, 2011). It is caused by the absent expression of paternally-inherited genes in the PWS region on 15q11-q13 (Ledbetter et al., 1981). While it presents with generalized hypotonia and developmental delay in infancy, PWS then manifests with uncontrollable appetite, hyperphagia, and excessive weight gain leading to severe obesity (Grechi et al., 2012).

Clinically, PWS patients suffer a complex pattern of physical, behavioral, endocrine, and intellectual deficiencies. Endocrine abnormalities lead to hypogonadism and short stature. In particular, growth hormone deficiency is reported to occur in 40% to 100% of the population (Griggs et al., 2015) and is commonly treated with growth hormone (Angulo et al., 2015). Behavioral disorders include obsessive compulsive behaviors such as skin picking, hoarding, re-doing, and repetitive speech (Griggs et al., 2015).

However, it is the appetite behavior classified as hyperphagia in Prader-Willi Syndrome that is the most life threatening (Dykens et al., 2007; Griggs et al., 2015) and until recently, no patient lived over the age of 50 due to morbid obesity and its related complications (Aycan et al., 2014). The mortality rate in patients with PWS is six times higher than patients with other intellectual disabilities (Einfeld and Kavanagh, 2006) and mortality in patients not treated with growth hormone was estimated to be 3% per year between the ages of 6 and 56 compared to the general population mortality of 0.13% below 55 years. Mortality in Prader-Willi Syndrome below 5 years of age has not been determined (Eiholzer, 2005).

Hyperphagic behaviors can also be dangerous in persons who are not obese, with increased risks of death due to choking while sneaking food, and gastric perforations after consuming more food than usual (Dykens et al., 2007). Approximately 8% of deaths in individuals with PWS are reported due to the choking, especially on hot dogs (Stevenson et al., 2007). PWS patients also are known to eat discarded (contaminated) food and items that are not for human consumption such as pet food, or even non-food items such as paint or paper (Griggs et al., 2015).

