6.2.6. Adverse Events and Serious Adverse Events

6.2.6.1. Definition of Adverse Events

An AE is defined as any untoward medical occurrence in a patient administered a pharmaceutical product during the course of a clinical investigation. An AE can therefore be any unfavorable

and unintended sign, symptom, or disease temporally associated with the use of an investigational product, whether or not thought to be related to the investigational product.

Patients will be monitored throughout the study for AEs. Monitoring for treatment-emergent AEs (TEAEs) will begin as soon as the patient is dosed. All AEs must be followed until they are resolved or stabilized, or until all attempts to determine resolution of the event are exhausted. The investigator should use their discretion in ordering additional tests as necessary to monitor the progress of such events.

An AE may be:

- A new illness, not documented in the patient's medical history;
- Worsening of a concomitant illness;
- An effect of the study medication; it could be an abnormal laboratory value, as well as a significant shift from baseline within normal range which the qualified investigator or medical qualified designate considers to be clinically important;
- A combination of two or more of these factors.

Surgical procedures themselves are not AEs. They are therapeutic measures for conditions that require surgery. The condition for which the surgery is required is an AE, if it occurs or is detected during the study period. Planned surgical measures permitted by the clinical study protocol and the condition(s) leading to these measures are not AEs, if the condition(s) was (were) known before the start of study treatment. In the latter case, the condition should be reported as medical history.

Weight gain or loss will not be recorded as an AE. Hyperphagia behaviors and skin picking will not be recorded as AEs; however, any other behaviors may be recorded as AEs based on the Investigator's opinion.

Patients will be monitored throughout the study for AEs. All AEs must be followed until they are resolved or stabilized, or until all attempts to determine resolution of the event are exhausted. The investigator should use his/her discretion in ordering additional tests as necessary to monitor the progress of such events.

Adverse events reported prior to dose administration will be recorded as part of the patient's medical history.

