8.6.4.5. Physical Examination Findings

Physical examination body systems will be presented as the number and percentage of patients that have normal or abnormal results at Screening, Placebo Lead-In, Titration, Treatment, Maintenance, and Follow-Up periods. The following body systems will be included:

- EENT (Eyes, Ears, Nose, Throat)
- Heart
- Peripheral vasculature
- Lungs
- Musculoskeletal system
- Abdomen
- Neurologic function
- Endocrine system
- Skin

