7.9 Interim Analysis

No interim analysis will be performed for this study.

8. Changes in Planned Analysis

Not applicable.

9. Data Issues

Not applicable.

Statistical Analysis Plan

Sponsor Name: Insys Development Company, Inc.
Sponsor Protocol ID: INS011-16-085

Covance Study ID: 000000163564

Approved

Statistical Analysis Plan

Sponsor Name: Insys Development Company, Inc.

Sponsor Protocol ID: INS011-16-085

Covance Study ID: 000000163564

10. References

- de Lauzon, B., Romon, M., Deschamps, V., Lafay, L., Borys, J., Karlsson, J., et al. (2004). The Three-Factor Eating Questionnaire-R18 is Able to Distinguish among Different Eating Patterns in a General Population. *Journal of Nutrition*, *134*, 2372-2380.
- Stone, A. A., Broderick, J. E., Junghaenel, D. U., Schneider, S., & Schwartz, J. E. (2016). PROMIS fatigue, pain intensity, pain interference, pain behavior, physical function, depression, anxiety, and anger scales demonstrate ecological validity. *Journal of Clinical Epidemiology*, *74*, 194-206.
- Varni, J. W., Magnus, B., Stucky, B. D., Liu, Y., Quinn, H., Thissen, D., et al. (2014). Psychometric properties of the PROMIS® pediatric scales: precision, stability and comparison of different scoring and administration options. *Quality of Life Research*, *23*(4), 1233-1243.

Statistical Analysis Plan

Sponsor Name: Insys Development Company, Inc.
Sponsor Protocol ID: INS011-16-085

Covance Study ID: 000000163564

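### SAP 7.7.6 counts abnormal physical examinations at baseline and post-baseline without linking them within patients, so newly abnormal patients are only bounded from below; a shift table would count them.

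*SAP*

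**What the plan says.** SAP 7.7.6 plans two outputs. The first is a listing: "Physical examination results (normal/abnormal) and details of abnormalities will be listed for the Safety population". The second is a table, set out separately per system examined, in which "the number and percentage of patients with abnormalities at baseline and post-baseline will be summarized by treatment group for the Safety Population". It names no visit, no period, no shift and no category for new or worsened findings.

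SAP 7.1 defines baseline as the last measurement before the first double-blind dose and limits summary tables to scheduled post-baseline visits. It does not say whether several post-baseline examinations are to be shown separately, pooled, or reduced to the worst or last.

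Protocol 8.6.4.5 plans a different layout, the "number and percentage of patients that have normal or abnormal results at Screening, Placebo Lead-In, Titration, Treatment, Maintenance, and Follow-Up periods", for nine named body systems including skin and endocrine. SAP Section 8, headed "8. Changes in Planned Analysis", reports nothing to declare.

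Elsewhere in the SAP, laboratory data (7.7.3.1) and the ECG assessment (7.7.5) each get a shift from baseline to every post-baseline visit.

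**The concern.** The purpose of a post-baseline safety table is to show what appeared or got worse on treatment, by arm. Two unlinked counts do not do that directly. A child abnormal in a system at both times enters both counts. A child whose abnormality resolves can offset another who becomes abnormal, leaving the totals unchanged.

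This matters more where patients enter with findings. Protocol 1.4 describes endocrine abnormalities, and it says: "Behavioral disorders include obsessive compulsive behaviors such as skin picking, hoarding". Both skin and endocrine system are examined. Protocol 6.2.6.1 adds: "Hyperphagia behaviors and skin picking will not be recorded as AEs". Adverse event tables therefore do not fully stand in for the skin examination. At stake is a readable comparison by arm of new examination findings. Efficacy, alpha and power are not involved.

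**Working it through.** The plan gives no figure to reproduce here, so the check is what the two planned counts can identify.

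**Inputs.** N = 33 patients per arm (SAP 2.3). Examinations take place at Visits 1 to 10 (Protocol 6.2.2 and Table 1), so Visits 4 to 10 give up to seven after baseline. The baseline counts b below are assumptions; the documents give no abnormality rate by body system.

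**Formula.** Let b be the number abnormal at baseline, p the number abnormal post-baseline, r the number abnormal at baseline but not post-baseline, and n the number newly abnormal. Then p = b − r + n, so n = p − b + r. The table prints b and p but not r. Hence n lies between max(0, p − b) and min(p, N − b).

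| Abnormal at baseline (b) | Abnormal post-baseline (p) | Possible newly abnormal (n) |
|---|---|---|
| 3 (9%) | 3 | 0 to 3 |
| 10 (30%) | 10 | 0 to 10 |
| 17 (52%) | 17 | 0 to 16 |
| 17 (52%) | 20 | 3 to 16 |
| 23 (70%) | 23 | 0 to 10 |
| 28 (85%) | 28 | 0 to 5 |

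**A less extreme case.** With b = 17, suppose 4 patients resolve and 4 become abnormal: p = 17 − 4 + 4 = 17. The table shows no change, while 4 of the 16 patients normal at baseline (25%) are newly abnormal.

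**Between arms.** If one arm goes from 17 to 20 and the other from 17 to 17, the ranges are 3 to 16 and 0 to 16. They overlap almost entirely, so the arms cannot be ranked on new abnormalities without an assumption about r.

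**Worsening.** A patient already abnormal in a system adds one to b and, if still abnormal, one to p, whether the finding is stable, worse or joined by a second one. In the rows above that applies to between 9% and 85% of the arm.

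**Wording.** SAP 7.7.3.1, 7.7.4 and 7.7.5 each say that results are summarized by visit; 7.7.6 does not. SAP 7.1, however, makes by-visit tables the default where applicable. Either reading is open. The missing link between baseline and later results is common to both.

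**The case against.** Several stronger conclusions are tempting, and the documents do not support them.

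- **That the table cannot show new findings.** A rise from b to p proves at least p − b newly abnormal patients, and if every baseline abnormality persists (r = 0) the count is exact. For example, with 80% abnormal at baseline and 82% versus 88% post-baseline, persistence gives (82 − 80)/20 = 10% and (88 − 80)/20 = 40% newly abnormal. The listing also lets each patient be traced.
- **That skin examination is the only planned table where worsening skin lesions could appear.** Protocol 6.2.6.1 excludes the picking behavior, not skin conditions in general, and it counts worsening of a concomitant illness as an adverse event. SAP 7.7.2 tabulates treatment-emergent events, including those that worsen, by arm and severity. A lesion attributed wholly to picking may still go unrecorded.
- **That both arms will show nearly the same high percentage.** Protocol 1.4 is qualitative, and it places generalized hypotonia in infancy. Nothing states what examiners will find at ages 8 to 17.
- **That seven examinations are pooled against one.** This is one plausible reading of 7.7.6, not its text.
- **That restoring the protocol layout would solve the problem.** Protocol 8.6.4.5 also plans unlinked counts, and it names a Follow-Up period although no examination is scheduled at Visit 11 (Protocol Table 1 and 7.6.1). Protocol Section 8 leaves detailed methods to the SAP.

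It is also fair to say that with about 66 patients the listing can be read by hand, that safety analysis is descriptive, and that a normal/abnormal shift table does not itself show worsening. All of this stands and limits the point. It does not supply the missing comparison by arm, which a listing does not provide.

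**Conclusion.** The point holds in a limited form. As specified, the table gives a lower bound on newly abnormal patients, exact only if no baseline abnormality resolves, and it does not register worsening within an already abnormal system. The gap can be wide (0 to 16 of 33 in the middle of the assumed range) or narrow (0 to 3 where few patients are abnormal at entry). How often abnormalities are present at entry, and how often they resolve, is not given in the documents.

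Two further points rest on the text alone: the handling of multiple post-baseline examinations is undefined, and the by-period layout of Protocol 8.6.4.5 is not carried over while SAP Section 8 declares no change. The consequence is confined to descriptive safety reporting. The change is worth making because a better table can be built from data already collected.

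**What to change.** 1. In SAP 7.7.6, define post-baseline by naming the scheduled visits included and how multiple examinations are reduced to one result.
2. Replace the two counts with a shift table by body system and arm: baseline normal or abnormal against worst post-baseline result, with a missing category. Report newly abnormal patients with those normal at baseline as the denominator. State this in the table shell, because the SAP 7.1 default is the whole analysis population. Show counts beside percentages, since the denominator may be small (5 patients if 28 of 33 are abnormal at baseline).
3. Optionally, count patients with a new or worsened finding from the recorded abnormality details. This is the only step that captures worsening.
4. Record the departure from Protocol 8.6.4.5 in SAP Section 8.

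The cost is SAP wording and one re-programmed table, with no new data; step 3 adds a modest review of free text, best done before unblinding. One limitation remains: the worst of up to seven examinations is set against a single baseline, so the newly abnormal row should be read as a comparison between arms.
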